### **Power analysis**

This study is not powered to detect small differences between treatment conditions, nor is it powered to detect differences on our dichotomous outcomes. We performed power analyses only for our primary outcomes, which were continuous measures of LSAS and SPD-SC. MLM allows the inclusion of all subjects with at least one data point, regardless of missing data and regardless of whether they drop

out. Thus, we based our power analysis on 156 participants and conservatively assumed that, on average, we will obtain 5 out of the 7 total assessments from each subject. The power analyses were calculated using the program PinT 2.12 (Power in Two Level Models).

For our main outcome analysis, we used our similarly sized DCS trial to estimate the variances and covariances required by PinT, and calculated detectable effect sizes for both LSAS and SPD-SC. PinT indicated we would have a power of .80 to detect an effect size as low as  $d=.296$ , between a small ( $d=.20$ ) and a medium ( $d=.50$ ) effect size. This translates into a difference of 6.59 points on the LSAS and .42 points on the SPD-SC (at post-treatment, 1-month follow-up, or 3-month follow-up). For the Fournier moderator analysis, we assumed five simultaneous moderators in each group, and included their 15 interactions with the 3 dummy variable contrasts. Moderators were modeled as predictors of both the intercept and slope. Using our prior DCS study to calculate the variances and covariances required by PiNT, we found that, with .80 power, we could detect an effect size of  $d=.466$ , slightly smaller than a medium effect size.

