### Participants

Our sample will consist of 156 participants for the clinical trial portion of the study, with a subset of 96 participants completing the optional laboratory-based fear extinction paradigm. Recruitment will be split amongst the three study sites: Boston University, University of Texas at Austin, and Rush University Medical Center. Inclusion and exclusion criteria are listed in Table 1.

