## **Screening and Randomization**

Individuals interested in the study will undergo a psychiatric evaluation to evaluate psychiatric inclusion and exclusion criteria. Participants will be medically cleared by a study physician.

Participants in the optional fear extinction retention experiment will be randomized to receive either DCS or placebo prior to fear extinction procedures. For the clinical trial portion of the study, participants will be randomized to one of four conditions: 1) tailored post-session DCS, 2) unselective pre-session DCS, 3) unselective post-session DCS, or 4) pill placebo. The conditions of the fear extinction experiment will be equally distributed across the four clinical trial conditions such that participants will be equally likely to receive any combination of fear extinction condition and trial condition. Randomization will occur by site using variable-sized permuted block randomization (block sizes varying from 4 to 12). Randomization tables will be created before the first subject is run and sent to the study pharmacist to make the appropriate medication kits. The statistician will check the balance of randomization to control for any unbalanced factors.

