## Data Analysis

We will assess the equivalence of the treatment groups on key baseline variables and any variables that differ among groups will be used as covariates in the final analyses. We will examine missing data patterns, dropout rates, and distributional properties of measures and use transformations to improve distributions if necessary. We will use pattern mixture modeling to assess the effect of missing data. We will rerun our analyses coding for various missing data patterns (no missing data, sporadic

missing, dropouts, etc.) to determine 1) if missingness impacts our findings and 2) how the differences between treatment conditions depends on the missing data pattern.

We will use multilevel modeling (MLM) to evaluate the effect of condition on our continuous outcome measures (LSAS, SPD-SC severity, MADRS, QLES-Q) and generalized linear mixed modeling (GLMM, which is MLM with a logistic linking function) to examine DCS's effect on the dichotomous outcomes ("response" and "remission," explained below). MLM is the recommended method for analyzing longitudinal psychiatric data, easily accommodates missing data, and allows inclusion of all subjects in the analysis even if they drop out. In our MLM analyses, the repeated assessments over time will be nested within individuals, which will be nested within treatment cohort, thereby appropriately accounting for correlated scores within cohorts. We will use a piecewise growth curve model, separately modeling change over time during treatment and follow-up. We will test for quadratic trends and include them if significant. Other non-linear models (e.g., exponential models) will be also be tested, and the model that best fits the data (based on AIC and BIC) will be used. Our "time" variable in these models will be coded as "assessment week" and will reflect the number of weeks since baseline. Using this model, we can test differences between tailored DCS administration and the 3 comparison groups (pre-session DCS, post-session DCS, and placebo) by including 3 dummy coded variables as predictors of the growth curve parameters. Each dummy variable will contrast tailored DCS to each of the other 3 conditions.

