### **Outcome Analysis**

In order to evaluate whether tailored DCS administration produces superior outcomes to pre-session DCS, post-session DCS, and placebo, we will examine if the dummy variable contrasting tailored DCS to the relevant comparison condition is a significant predictor of the intercept. We will alternately "center" the "assessment week" variable at either posttreatment, 1-mo FU, or 3-mo FU to test for significant differences between conditions at each of these time points.

We will also examine a number of possible moderators of the potential superiority of tailored DCS over the comparison conditions (and, secondarily, of the superiority of pre-and post-DCS administration over PBO). We will use the Fournier approach to identify important moderators. This approach uses an algorithmic method to select significant predictors and moderators within each group of potential moderators (e.g., demographics, clinical and personality characteristics). These selected moderators are then combined in a final analysis, which identifies moderators that are significant over and above the other potential moderators. This approach strikes a balance between testing each moderator separately (which substantially increases Type I error due to the multiple tests) and testing all moderators simultaneously (which may substantially increase the likelihood of Type II error).

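### The stated .80 power at d=.296 (6.59 LSAS points) does not hold for the pairwise contrasts the plan tests; under stated assumptions power there is about .26 to .38.

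*Combined protocol and SAP*

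**What the plan says.** The Participants section sets the size: "Our sample will consist of 156 participants for the clinical trial portion of the study". Under Screening and Randomization, "participants will be randomized to one of four conditions", with wording that implies equal allocation.

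The Data Analysis section specifies a piecewise growth model with separate treatment and follow-up phases. It compares tailored DCS with pre-session DCS, post-session DCS and placebo "by including 3 dummy coded variables as predictors of the growth curve parameters". Each dummy sets tailored DCS against one other arm. On baseline imbalance it says that "any variables that differ among groups will be used as covariates in the final analyses".

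The Outcome Analysis section gives the test: "we will examine if the dummy variable contrasting tailored DCS to the relevant comparison condition is a significant predictor of the intercept", with time centred in turn at post-treatment, 1 month and 3 months.

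The Power analysis section states, for the main outcome analysis: "we based our power analysis on 156 participants and conservatively assumed that, on average, we will obtain 5 out of the 7 total assessments". It continues: "PinT indicated we would have a power of .80 to detect an effect size as low as" d=.296. It then converts this to raw units: "This translates into a difference of 6.59 points on the LSAS and .42 points on the SPD-SC (at post-treatment, 1-month follow-up, or 3-month follow-up". The variances and covariances came from a prior trial and are not printed. Alpha, sidedness, the SD behind d and the number per arm are not printed either.

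**The concern.** The power statement is built on 156 participants, but each primary contrast uses two of the four arms, about 78 people. An effect of d=.296 is small for 39 against 39, and the planned model leaves the arms free to differ at baseline, so it does not gain the precision of a baseline-adjusted comparison. A single detectable value is also given for three time points, although the precision of a growth-model intercept changes with the centring point and is poorest at the last visit.

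This is the only power statement for the primary outcomes. A reader who accepts it would take a null result as evidence against a benefit of about 6.6 LSAS points. If the detectable difference is about twice that, the trial cannot support such a reading.

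**Working it through.** **Inputs from the plan.** N=156; four arms, so 156/4 = 39 per arm (equal allocation inferred); pairwise contrast on the intercept; stated d=.296, 6.59 LSAS points and .42 SPD-SC points.

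**Assumptions, because the plan is silent.** Two-sided 5% test; constant SD; compound symmetry with between-person share ρ of .5 to .9; weekly sessions; nine LSAS assessments from Table 3 without the screening visit, at weeks 0 to 6, 10 and 18, all observed. Cohort clustering and multiplicity are ignored. Complete data and no clustering both favour the plan.

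**The plan's own figure.** The implied SDs are 6.59/.296 = 22.26 LSAS points and .42/.296 = 1.42 SPD-SC points. The .80 power at d=.296 cannot be reproduced because the program's inputs are not printed.

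**Simple two-group test.**
- Detectable d = (1.9600 + .8416) × √(2/39) = 2.8016 × .2265 = .634, or .634 × 22.26 = 14.1 LSAS points.
- Power at .296 = Φ(.296/.2265 − 1.96), plus a negligible opposite tail, = .257 (t-based .252).
- n per arm for .80 power = 2 × 2.8016²/.296² = 179.2, so 180.
- Even 78 against 78, using everyone in one contrast, gives 2.8016 × √(2/78) = .449.

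**What repeated measures would have to deliver.** Let f be the share of the endpoint variance that remains. For .80 power at d=.296 with 39 per arm, f = .296² × 39/(2 × 2.8016²) = .218. That is an effective SD of 22.26 × √.218 = 10.4 LSAS points.

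**The planned piecewise model.** For visit week t the design row is (1, min(t,6)−6, max(t−6,0)), with V = ρJ + (1−ρ)I (J all ones, I the identity). Then f = c′(X′V⁻¹X)⁻¹c, with c = (1,0,0) at post-treatment, (1,0,4) at 1 month and (1,0,12) at 3 months. Detectable d = 2.8016 × √(2f/39), and n per arm = 179.2 × f.

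| | Post-treatment | 1 month | 3 months |
|---|---|---|---|
| f, ρ=.5 | .696 | .620 | .958 |
| f, ρ=.9 | .939 | .924 | .992 |
| Detectable d, ρ=.5 | .529 | .500 | .621 |
| Detectable d, ρ=.9 | .615 | .610 | .632 |
| LSAS points | 11.8–13.7 | 11.1–13.6 | 13.8–14.1 |
| SPD-SC points | .75–.87 | .71–.87 | .88–.90 |
| Power at .296 | .27–.35 | .27–.38 | .26–.27 |
| n per arm for .296 | 125–168 | 111–166 | 172–178 |

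The smallest f in the table is .620, against the .218 required.

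**Sensitivity** (post-treatment / 1 month / 3 months)
- Quadratic term in the treatment phase: .565–.621 / .514–.612 / .622–.632.
- Post-treatment at week 5 or 7: .52–.61 / .50–.61 / .62–.63.
- Zero within-person correlation (unrealistic): .397 / .311 / .607.
- One-sided 5%: .47–.55 / .44–.54 / .55–.56, with power .37 to .51 at d=.296.
- Five of seven assessments (assumed weeks 0, 2, 3, 4, 6, 10, 18; ρ from .3 to .7): power .27 to .30 at post-treatment.
- Baseline constrained equal across arms: .424 / .368 / .488 at ρ=.5 and .211 / .184 / .228 at ρ=.9. Reaching .296 needs ρ of .795 / .720 / .829.

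**The case against.** The strongest reply is that the stated value came from dedicated software fed with prior-trial variances we cannot see, so the plan's number is not shown to be a computing error. That is right, and no software error is claimed. The printed figures also agree with one another.

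The second reply is that a common baseline is a natural option in a randomized trial, and the .83 it needs lies inside the 50 to 90% range used here. This also stands as far as it goes: if that was the model powered, .296 may be attainable. But the dummies predict the growth parameters, and baseline variables become covariates only where the groups differ, so the plan as written leaves the baselines free.

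Third, the calculation uses nine complete visits where the plan assumes on average five of seven, and it omits the cohort level. Both choices flatter the plan's power, so they make the ranges illustrative without rescuing .296.

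Finally, the plan already says that it is not powered for small differences. That caveat still leaves readers believing that d=.296 is detectable.

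**Conclusion.** The concern holds. For the pairwise contrasts and the model the plan describes, .80 power at d=.296 is not supported at any of the three time points. On a two-sided 5% test with the assumptions listed, power at d=.296 is about .26 to .38, and the detectable effect is about .50 to .63, or 11 to 14 LSAS points.

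The 3-month figure is the firmest. With constant variance and complete data it cannot exceed .634, and it stays at .61 to .63 for within-person correlations from 0 to .9. The post-treatment and 1-month figures depend more on the unprinted variance components. A one-sided 5% test does not close the gap at realistic correlations. Of the variants tested, only the common baseline with a between-person share of about .83 or more reaches .296 at all three points.

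**What to change.** Keep n=156 and the planned analysis. Rerun the power calculation for a single tailored-versus-comparator contrast at about 39 per arm, with the piecewise model, the Table 3 schedule and each of the three centring points. In the Power analysis section, print alpha and sidedness, the number per arm, the SD that defines d, and the variance components from the prior trial. Replace .296, 6.59 and .42 with the resulting values for each time point. If a one-sided test or a common baseline was intended, say so in the Data Analysis section and power that model. Recheck the moderator figure of d=.466 with the same inputs; no replacement is offered for it here.

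The cost is one recalculation from data the team already holds and a reworded paragraph. No extra participants are needed, but the stated figure is likely to be less favourable.

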### **Data and Safety Monitoring Board (DSMB)**

A Data and Safety Monitoring Board (DSMB) will be created to ensure that the safety of study subjects is protected, and the scientific goals of the study are being met. The DSMB will review any proposed amendments to the study protocol, perform expedited monitoring of all serious adverse events, perform ongoing monitoring of drop-outs and non-serious adverse events, determine whether study procedures should be changed or the study should be halted for reasons related to the safety of study subjects, and perform periodic review of the completeness and validity of data to be used for analysis of safety and efficacy. The DSMB will ensure subject privacy and research data confidentiality.

### **Collection and Reporting of AEs and SAEs**

AE information will be obtained by questioning subjects. All new complaints must be recorded. Pre-existing complaints or symptoms that increased in intensity/frequency after having signed the Informed Consent Form must be recorded. All AEs must be characterized in terms of their start/stop dates, start/stop times, intensity, action taken on Intervention, relationship to Intervention, subject outcome and whether or not the AE led to a Serious Adverse Event (SAE). Clinically relevant changes to the intensity/frequency of a reported AE requires a separate entry on the AE Form.

A Serious Adverse Event (SAE) is defined as any untoward medical occurrence that:

- Results in death;
- Is life-threatening;
- Requires in-patient hospitalization or prolongation of existing hospitalization;
- Results in persistent or significant disability/incapacity
- Is a congenital anomaly/birth defect.

All serious events occurring between signing of the Informed Consent Form by the subject and signing of the End of Trial Form by the investigator, except those pre-specified in the protocol, must be reported as soon as practical (within 24 hours of awareness) to the IRB and the DSMB.

